## Study 1 Intervention

Qualifying participants will be stratified by age and motor symptom severity as assessed by the UPDRS (UPDRS Motor score (+/- 4 points) and then randomly assigned to either the in-home cycling group or the waitlist control group.

For individuals assigned to the control group, pre-testing will occur six-months before the baseline measures are collected (figure 1). This period will allow us to collect normal care control data from each participant prior to their six months in the active phase of the study. During this period, each individual will be contacted weekly by the study team to complete a falls questionnaire. Baseline testing will occur within two weeks of the start of the Intervention. Post-test data will be collected following the 6-month intervention and will occur within 1 week of the last calendar day of the intervention.

Participants will be asked to not begin any new exercise programs once enrolled in the study, but will not be asked to discontinue any current physical activity. Information about current physical activity level will be collected at all time points.

Activity monitors (Garmin VivoSmart 3) will be donned by all study participants throughout the duration of the study starting at the time of either pre-test or baseline assessment depending on group assignment and continuing through the 3-month follow-up. These devices allow for activity monitoring as well as online monitoring of heart rate. Participants will be asked to wear the activity monitors at all times once enrolled in the study. Number of steps taken daily and amount of aerobic activity will be used to compare changes in activity level.

**Cycling** -The initial cycling session will occur in the participant's home within 2-weeks of the baseline assessment. Two members of the testing team will be present. The team will set-up the bike and properly fit it to the individual rider. Additionally, the team will ensure the stationary bike is set-up in a safe and secure manner and in an area free of clutter and dangerous obstacles. Study team member will also set-up and establish a secure connection using the MiFi device at this time. Both groups will be provided with a MiFi wireless internet connection if needed to allow for data collection of cycling and activity monitor data.

A tablet will be installed and mounted to the recumbent bike. A remote connection will be made to an individual at the UW to test the Skype connection and show the participant how to use the technology. This testing will lessen the likelihood of study dropout due to frustration with the technology component. An additional failsafe has been built into the computer system which allows us to remotely control the software and assist the participant if necessary. For privacy, we will not be able to access the machine without the participant clicking the allow button on the screen.

The selected recumbent bike has been chosen based on a number of factors which make it safe, user friendly and allow for the tracking of the desired speed and duration data. The bike weighs over 100 pounds and has a wide footprint to prevent tipping as well as a low ground clearance step through to allow individuals with PD to get on and off the bike without falling. The saddle is a wide padded seat with a fully supportive backrest to promote comfort but also maximize rider safety. Pulse sensors are located on the display mount

[figure not shown]

Figure 1. Movement of participants through the study.

and seat handles and pulse readings are incorporated into the software which allows for real-time tracking of the speed and resistance settings of the cycle. Additionally, this bike comes with a large digital display and preprogrammed cycling sessions that will allow a programmed and progressive exercise plan to be implemented after the 6-month group cycling program ends.

Scheduled training sessions will occur in the individual's home with digital display connecting the individual with PD to a member of the research team. Training sessions will occur three times per week for 6 months. Each training session will consist of up to 30 minutes of cycling at a target speed with a 2-minute warm-up session, and a 2-minute cool down at the end of the session. Actual intervention times will be based on the individual's endurance level and will increase over the sessions. The initial target speed will be at 110% of the average pace established by the individuals during the first testing session (10% above the self-selected velocity). Target velocities for future training sessions will be based upon the average of the previous week's training sessions. It will be the job of the research assistant to help the individual attain and maintain their target velocity during testing.

When beginning the cycling sessions, participants will have their maximum and target heart rate calculated. The calculation for target heartrate is  $220 - \text{participant age}$ . Target heartrate will be calculated using a span of 50-85% of the calculated maximum (50 to 70% of maximum = moderate and 70 to 85% of maximum = vigorous exercise). Individuals will be provided with a printout of these calculations as well as the weekly exercise goals established by the Centers for Disease Control and Prevention and the American Heart Association (see Appendix I and II). Participants will not be instructed to cycle on the days without scheduled cycling sessions, but they will be informed of the CDC and American Heart Association recommendations and told that they are invited to use the bike outside of the scheduled sessions. All participants will be asked to complete a daily exercise log (Appendix III). Logbooks entries will be collected from all participants at four-week intervals and reviewed by the study team.

Participants will be provided with an information sheet to describe the cycling sessions, their target heart rate, perceived exertion and the exercise journal (appendix V, "In-Home Cycling Program – Partnered Cycling - ") and the one page "How much physical activity do you need" document from the American Heart Association. For those in the partnered cycling group, we will gradually increase the duration of the cycling sessions for the first 12 weeks while verbally coaching them to keep their heart rate between 50 and 70% of their calculated maximum. The sessions during the first week will last 5 minutes. As the individual exercises, it will take a greater speed to attain the desired heart rate. For the second twelve weeks, the research assistant will help the participants to monitor the average speed of the final session of the previous week and suggest an increase in the target speed to increase the individual's heart rate. The research assistant will also assist the individual in monitoring their heart rate to stay in the upper end of the target intensity range. The goal durations and intensities for each week are listed in table 1.

Week	Target Duration	Target Intensity
1	5 mins	50 – 70% of max heart rate
2	10 mins	50 – 70% of max heart rate
3	12 mins	50 – 70% of max heart rate
4	15 mins	50 – 70% of max heart rate
5	17 mins	50 – 70% of max heart rate
6	20 mins	50 – 70% of max heart rate
7	20 mins	50 – 70% of max heart rate
8	22 mins	50 – 70% of max heart rate
9	25 mins	50 – 70% of max heart rate
10	25 mins	60 – 70% of max heart rate
11	30 mins	50 – 70% of max heart rate
12	30 mins	60 – 70% of max heart rate
13	30 mins	60 – 70% of max heart rate
14	30 mins	60 – 70% of max heart rate
15	30 mins	60 – 70% of max heart rate
16	30 mins	60 – 70% of max heart rate
17	30 mins	60 – 70% of max heart rate
18	30 mins	60 – 70% of max heart rate

19	30 mins	60 – 70% of max heart rate
20	30 mins	60 – 70% of max heart rate
21	30 mins	60 – 70% of max heart rate
22	30 mins	60 – 70% of max heart rate
23	30 mins	60 – 70% of max heart rate
24	30 mins	60 – 70% of max heart rate

During the first testing session of each week a study team member will complete a falls assessment with each individual.

Normal Care Control - Individual assigned to the control group will be advised to continue their daily routines during the first 6-months. Following this period, they will complete a baseline assessment and crossover into the cycling group. This period will allow us to collect normal care control data from a randomly assigned, age and disease severity (+/-4 points) matched individual. During this period, each individual will be contacted weekly by the study team to complete a falls questionnaire.

Health Coach: Following completion of the 6-month in-home cycling program, participants will be asked to continue their training program following the same training regime. Half of the individuals in the study will have been randomly assigned within their strata to a health coach mediated maintenance program while the remaining individuals in the strata will be assigned to the self-motivated program. Individuals in the health coach group will be introduced to their assigned health coach during the final week of the 6-month intervention and a schedule of meeting times will be determined. Individuals will meet with their health coach once every other week for 15-minutes during their cycling sessions. Individuals in both groups will be taught how to access the built-in programming options on the bike which allow for use of customized training programs. We will set-up the training program for each individual and make sure that they are fully able access the module. During this period, each individual will continue to be contacted weekly by the study team to complete a falls questionnaire.

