### **Research Design**

This pilot study will utilize two separate experimental designs to address: 1) the Reach, Effectiveness, Implementation and Maintenance and 2) the optimal delivery method for an in-home exercise intervention program for individuals with PD living in underserved communities. Both studies will utilize paired, randomly assigned groups to explore the given questions. Pairs will be based on disease severity (UPDRS III scores) and age.

Study 1: The proposed pilot study will utilize the RE-AIM framework (Reach, Effectiveness, Adoption, Implementation and Maintenance) to focus on the reach and effectiveness of a 6-month triweekly in-home cycling program and then pilot a health coach model to promote maintenance for the subsequent 3-month period. 40 qualified individuals will be paired based on disease severity (score on subsection III of the UPDRS) and age and randomly assigned to either the cycling group or the normal care control group for 6 months. For those in the cycling group, participants will interact via Skype with study team members during all cycling sessions. This intervention will allow the individuals enrolled to participate in regular exercise and a community activity that promotes social support and engagement. The proposed pilot maintenance model for the 3-month period following the intervention will implement a health coach model with scheduled sessions every other week to discuss goals and motivation while decreasing the total contact time with the participant. Individuals in the normal care control group will crossover and complete the cycling intervention following the initial 6 months.

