## Power and Statistical Analysis

As this is a pilot study, we have not proposed a recruitment level that will properly power the outcome measures for a desired effect size. Previous work by [name] during her post-doctoral training under the guidance of [name] at Washington University in St. Louis indicate that approximately 27 individuals per group are needed to provide 89% power to detect differences in a similar intervention at a significance level of 0.05. This estimate uses gait velocity as the primary variable of interest and relies on a previous measured average forward gait velocity of  $1.2 \pm 0.1 \text{ m/s}$  and an average backward gait velocity of  $0.6 \pm 0.1 \text{ m/s}$  for 60 individuals with PD. The estimate is designed to detect a difference of 1 SD or  $0.1 \text{ m/s}$ , which is equivalent to an effect size of 0.4. Additionally, an attrition rate of approximately 15-20% should be expected. As the future RCT will likely focus on spatiotemporal measures collected during ADL task performance, this estimate provides some guidance for future work, but ideally future proposals will be powered from pilot data on the aims proposed herein. The proposed study of 40 individuals (20 per group) will provide pilot data which will be used to estimate effect size for the subsequent proposal (study 1).

To examine the reach of the project into the lower SES Parkinson disease community, we will analyze questions 6 and 7 of the MacArthur Scale of Subjective Social Status. A descriptive analysis of these data and subsequent comparison to income data for the state of WI will allow us to assess if individuals with PD in lower SES communities were optimally targeted.

To examine the qualitative effectiveness of the cycling intervention as well as the health coach intervention we will code the responses from the survey, assess common themes and use these data to inform the development of a larger RCT.

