For both studies, we will employ a  $2 \times 2$  repeated measures ANOVA with time and intervention as the factors, to determine the outcomes of the cycling intervention effectiveness aims. Additionally, we will use a time (posttest to 3-month follow-up) by group to examine the effectiveness of the health coach maintenance model. Variables of interest include: total number of completed sessions and session duration; PASS scores, walking velocity, stride length, base of support; gait variables (velocity, stride length, base of support and % of time in double support) and MiniBESTest scores as well as number of falls; and mean daily step count.

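### The Study 1 health-coach allocation has no stated balance by original arm and its analysis has no arm term, so a chance imbalance between immediate and wait-list participants would go unadjusted

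*Combined protocol and SAP*

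**What the plan says.** Study 1 has two allocations.

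- **First allocation.** Under Research Design, "40 qualified individuals will be paired based on disease severity (score on subsection III of the UPDRS) and age and randomly assigned" to cycling or to normal care control. Study 1 Intervention describes the same step as stratification: "Qualifying participants will be stratified by age and motor symptom severity as assessed by the UPDRS". The control is described there as "a randomly assigned, age and disease severity (+/-4 points) matched individual". The statistical section gives 20 people per group.
- **Timing.** "Individuals in the normal care control group will crossover and complete the cycling intervention following the initial 6 months". Counted from entry, the three-month maintenance period is therefore at about months 6-9 for immediate cyclists and months 12-15 for wait-list participants.
- **Second allocation.** In the Health Coach paragraph, "Half of the individuals in the study will have been randomly assigned within their strata to a health coach mediated maintenance program". The comparison group is then described in these words: "while the remaining individuals in the strata will be assigned to the self-motivated program". Original arm is not named as a factor. Figure 1, which shows participant flow, is not reproduced in the text available for review.
- **Analysis.** Under Power and Statistical Analysis, "we will use a time (posttest to 3-month follow-up) by group to examine the effectiveness of the health coach maintenance model". No term for original arm or period is listed.

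The maintenance clauses of Study 1 Hypotheses 2b and 2c predict that effects last with the coach but not in the solo group. Both rest on this comparison.

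**The concern.** Each matched pair holds one immediate cyclist and one wait-list participant. If the coach is split within the pair, the coached and self-motivated members always come from opposite arms. Balance of arm between the two coach groups then depends on how the splits fall across 20 pairs, and nothing in the text constrains it. If strata are larger than pairs, arm is still left to chance, only less so.

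This matters if the change from posttest to follow-up differs between those who maintain early and those who maintain six months later. Part of any such difference would then appear as a coach effect, or hide one, because the planned time-by-group comparison cannot separate the two. The stated purpose of the pilot is to supply effect sizes for a later proposal, so an avoidable error in the estimate would be carried forward.

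**Working it through.** The documents give no figure for the coach comparison. Their one power statement (27 per group, 89% power) is guidance for later work and is not used here.

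**Inputs from the documents.** 40 participants, 20 per original arm; half coached, so 20 against 20; strata formed from age and UPDRS motor score. Strata size is not stated beyond the reference to pairs, so larger sizes are assumptions.

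**Imbalance if strata are pairs.** Let X be the number of coached participants from the immediate arm. One member of each pair is coached at random, so X is Binomial(20, 0.5).

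- Exactly 10:10: 184,756 / 1,048,576 = 17.6%.
- 13:7 or worse in either direction: 2 × 137,980 / 1,048,576 = 26.3%.
- 14:6 or worse: 2 × 60,460 / 1,048,576 = 11.5%.

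**Imbalance if strata are larger (assumed sizes).** Within a stratum holding equal numbers from each arm, half of whom are coached, the coached immediate count is hypergeometric. Summing over strata gives:

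| Stratum size | SD of X | 13:7 or worse | 14:6 or worse |
|---|---|---|---|
| 2 (pairs) | 2.24 | 26.3% | 11.5% |
| 4 | 1.83 | 16.6% | 5.2% |
| 8 | 1.69 | 13.4% | 3.5% |
| 40 (one stratum) | 1.60 | 11.3% | 2.6% |

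Tight matching on age and UPDRS makes arm imbalance more likely than simply halving the 40, because every pair forces a choice between arms.

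**Share of an order difference that enters the estimate.** The coached group has X/20 immediate cyclists and the self-motivated group (20 − X)/20. The difference in proportions is (2X − 20)/20: at X = 13 it is 6/20 = 0.30, and at X = 14 it is 8/20 = 0.40. The unadjusted coach estimate carries that fraction of any between-order difference in posttest-to-follow-up change.

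**Attrition.** The plan expects 15-20%. If losses took out whole pairs, 17 or 16 pairs would remain, and the chance of a share of 0.30 or more would be 14% or 21%. Losses will not be so tidy: independent 20% loss leaves on average 20 × 0.8² = 12.8 intact pairs and 40 × 0.8 − 2 × 12.8 = 6.4 single members. These figures show only that drop-out does not remove the issue.

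**Cost of adjusting.** With r = (2X − 20)/20 the correlation between coach and arm, including arm inflates the variance of the coach effect by 1/(1 − r²): 1/(1 − 0.09) = 1.10 at 13:7 and 1/(1 − 0.16) = 1.19 at 14:6.

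**Effect of balancing the list.** If half of each arm is coached, X is fixed at 10, the share is 0 at assignment, and the chance of 13:7 or worse is 0%.

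**The case against.** A reader might infer that coach and order are confounded by design, since they coincide inside every pair. The documents do not support that. The coach is assigned at random, so the direction varies from pair to pair and the expected order contrast is zero. Complete confounding across 20 pairs has probability 2 × 0.5^20, about 0.0002%.

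A reader might also infer a seasonal bias in step count, with the two arms maintaining in opposite halves of the year. Six months is the lag from entry, and the documents describe no enrolment calendar. If pairs start at different times of year, seasonal differences between the orders take opposite signs and tend to cancel. Nor do the documents give any figure from which to size a seasonal effect in steps per day.

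Three further points have weight.

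- The wait-list member's extra test visit, longer monitor wear and six more months of disease act mainly on levels, which largely drop out of a posttest-to-follow-up change.
- The wording about remaining individuals in the strata fits strata larger than two, which lowers the probabilities, and the unseen Figure 1 might show a split within each arm.
- The effect is modest beside sampling error. With an order effect on change of 0.5 SD (assumed), a 13:7 split moves the estimate by 0.30 × 0.5 = 0.15 SD, against a standard error of √(1/20 + 1/20) = 0.32 SD.

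These points limit the concern to chance imbalance. They do not remove it: under every stratum size tried, a split of 13:7 or worse has at least an 11% chance, and the listed model would leave it unadjusted.

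**Conclusion.** The point holds as a cheap improvement. The text states no balance of the coach allocation by original arm and lists no arm term in the coach analysis. The result is an avoidable chance imbalance, left unadjusted, in a comparison of at most 20 against 20. Its probability at 13:7 or worse is 26% if strata are pairs and about 11-17% under the assumed larger strata. At that split, 30% of any between-order difference in change enters the estimate.

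This rests on reading silence about arm as absence of balance, and on the two arms reaching maintenance six months apart from entry. The size of the between-order difference is unknown, so the consequence can be stated only as a fraction of it. Only the maintenance clauses of Hypotheses 2b and 2c are affected. The baseline-to-posttest comparisons are not.

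**What to change.** 1. **Power and Statistical Analysis.** Add original arm and its interaction with time to the posttest-to-follow-up coach comparison. The interaction is needed because the coach effect is itself a difference in change; a main effect of arm alone adjusts only levels. Equivalently, model change on coach and original arm. This also covers imbalance that arises later through drop-out.
2. **Study 1 Intervention, Health Coach.** Constrain the coach list so that half of each original arm is coached. The age/UPDRS matching can stay. For example, choose 10 of the 20 pairs at random in which the immediate cyclist gets the coach, and give the coach to the wait-list member in the other 10. If strata are larger than pairs, halve each arm within the stratum as far as numbers allow.
3. **State the unit.** Say whether strata are pairs or larger groups. If Figure 1 already shows a split within each arm, say so in the text; item 1 then still applies.

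The cost is a slightly more constrained randomisation list and one model degree of freedom, with a variance factor of 1.10 should the analysed split be 13:7. No added participants, visits or coaches are needed.

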## Specific Aims

### **Study 1**

**SPECIFIC AIM 1:** Examine the reach and maintenance of an in-home cycling program for underserved individuals with PD. Reach will be assessed by examining the demographic characteristics of the individuals enrolled and through the administration of a questionnaire on objective and subjective socioeconomic status to better understand their level of accessibility to services, perceived barriers and economic status. We will also explore the implementation of a health coach to promote effective maintenance of the program after the 6-month intervention. Finally, we will conduct two interviews to better understand strengths and weakness of the program and to better address the needs of the participants in future studies.

**Hypothesis 1a:** Demographic characteristics including race and socioeconomic status of the enrolled participants will not statistically differ from the characteristics of the state of WI.

**Hypothesis 1b:** Feedback from participant interviews will inform future delivery of the in-home cycling program.

**SPECIFIC AIM 2:** Determine the effectiveness of a 6-month in-home, progressive, tele-exercise cycling program and 3-month health coach follow-up for underserved populations of individuals with PD.

**Hypothesis 2a:** Participants will improve performance of activities of daily living from baseline to posttest. These effects will be maintained at 3-month follow-up.

**Hypothesis 2b:** Participants will significantly improve measures of gait and balance performance and non-significantly improve fall rate from baseline to posttest. These effects will be maintained at 3-month follow-up in the group piloting implementation of a health coach, but not in solo follow-up group. Falls data will allow for effect size calculations for future applications.

**Hypothesis 2c:** Activity level as measured by an activity monitor will increase from baseline to posttest. This effect will be maintained at 3-month follow-up in health coach group, but not in the solo group.

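### Study 1's health coach comparison takes its starting value after the coach group knows its allocation and has met its coach

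*Combined protocol and SAP*

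**What the plan says.** Four statements about Study 1 fix the order of events.

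- **Allocation to coach or self-motivated follow-up** (Study 1 Intervention, Health Coach paragraph): "Half of the individuals in the study will have been randomly assigned within their strata to a health coach mediated maintenance program". No date is given.
- **First contact with the coach** (same paragraph): "Individuals in the health coach group will be introduced to their assigned health coach during the final week of the 6-month intervention", and at that point "a schedule of meeting times will be determined".
- **Posttest** (Study 1 Intervention): "Post-test data will be collected following the 6-month intervention and will occur within 1 week of the last calendar day of the intervention".
- **Analysis** (Power and Statistical Analysis): "we will use a time (posttest to 3-month follow-up) by group to examine the effectiveness of the health coach maintenance model".

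Research Design places the coaching after the cycling programme: "The proposed pilot maintenance model for the 3-month period following the intervention will implement a health coach model with scheduled sessions every other week". Hypothesis 2b in the Specific Aims states what the comparison should show for gait and balance: "These effects will be maintained at 3-month follow-up in the group piloting implementation of a health coach, but not in solo follow-up group". Hypothesis 2c expects the same pattern for activity level.

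**The concern.** The coach comparison is randomised, and its starting value should be measured before either group can respond to the allocation. Here the coach group has already been told, has met the coach and has meetings booked. No such contact is described for the self-motivated group before its posttest.

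The coach's role is to work on goals and motivation, and the listed outcomes depend on effort or behaviour: walking velocity and other gait measures, PASS, mini-BESTest and daily steps. If knowing that a coach is coming changes how hard a participant tries at posttest, or how much they walk beforehand, the change enters the starting value of one group only. The subtraction then removes it from the effect being estimated. Study 1 is meant to supply effect sizes for the next proposal, so a distorted estimate would carry forward.

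**Working it through.** The plan gives no figure for this point. Its only power statement (27 per group, 89%) concerns a different comparison and does not bear on it. The check is of timing, followed by some simple arithmetic.

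**Order of events, from the sections cited above**

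1. Allocation: made by the final week, on an unstated date.
2. Introduction to the coach and setting of meeting times: final week of cycling (week 24 of the training table).
3. Last day of the intervention.
4. Posttest: 0 to 7 days later.
5. Follow-up assessment at 3 months.

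Step 2 precedes step 4 for every coach-group participant who follows the schedule. No other section reverses this order or places the first coaching session relative to posttest.

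**Number affected**

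- Half of 40 is 20.
- With the protocol's expected attrition of 15-20%: 20 × 0.85 = 17 and 20 × 0.80 = 16.

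**How much coaching could precede posttest**

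- Sessions last 15 minutes and occur every other week. Taking 3 months as 12 to 13 weeks (an assumption), there are 12/2 = 6.0 to 13/2 = 6.5 sessions, or 90 to 97.5 minutes in total.
- None is scheduled before the intervention ends. The posttest window of up to 7 days is shorter than the 14-day interval between sessions, so at most one session can fall inside it.
- The share of planned coaching that could precede the starting value is therefore between 0 and about 1/6, or 17%.

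**Effect on the estimate**

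Let P and F be mean posttest and follow-up values, with subscripts c (coach) and s (self-motivated). The time-by-group contrast is

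D = (F_c − P_c) − (F_s − P_s).

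If early knowledge or contact shifts P_c by an amount e and leaves follow-up unchanged, the contrast becomes D − e. The loss is one for one. Randomisation does not remove it, because e arises after allocation. An early improvement (e > 0) makes the coach look less effective; a shift the other way would do the opposite. The documents contain nothing from which e can be estimated.

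**Protections in the plan**

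UPDRS III (Clinical measures) and the mini-BESTest (Measures of motor function) are recorded for blinded rating. That guards against rater bias but not against a change in participant effort. No blinded rating is described for PASS or gait. Activity monitors are worn throughout, but no averaging window is defined for the posttest step count, so it may include days after the introduction.

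**The case against.** The strongest reply is that the disturbance is slight. By the final week each participant has been scheduled for about 3 × 24 = 72 live sessions with a research team member. One introduction on top of that is unlikely to move gait speed, PASS or mini-BESTest by much. Meeting the coach before staffed sessions end is also a reasonable way to manage the handover. The study is an acknowledged pilot without formal power, and an early motivational gain would understate the coach's benefit, not create one.

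Most of this stands as an argument about size. It does not answer the point about order: the starting value still follows disclosure in one group, and that can be avoided without losing the handover.

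A reader might also infer that the 6-month comparison of cycling with normal care is compromised, since the same posttest closes it for the cycling arm. That comparison is already open to participants, so knowing a second allocation adds little, and I would not press it.

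**Conclusion.** The point holds as one of sequence. As written, the starting value of the coach comparison is measured after the coach group knows its allocation and has met its coach, and possibly after one of about six sessions. This affects all 20 planned coach participants (16 to 17 after attrition). Any early shift is subtracted in full from the estimated effect; its size is unknown and may be small.

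Three stronger readings are tempting, and the documents do not support them.

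- **That coaching has already begun at posttest.** The final-week contact is an introduction and scheduling, and the sessions belong to the following three months. The final week plus the posttest window could put up to about two weeks between introduction and posttest, but that is not two weeks of coaching.
- **That allocation is made in the final week.** The text says only that it has been made by then.
- **That disappointment lowers the self-motivated group's posttest.** No section says when that group learns its allocation. The participant flow figure and consent pages are not available here, so this cannot be settled.

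Nor can a percentage attenuation be given, since it would only restate an assumed early share of the effect.

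The verdict assumes that the introduction tells participants their allocation, which follows from meeting an assigned coach, and that the schedule is followed as written.

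**What to change.** Amend the Health Coach paragraph of Study 1 Intervention as follows.

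- State when the coach or self-motivated allocation is made. Disclose it to both groups, and introduce the coach, only after all posttest measures are complete, for example at the end of the posttest visit.
- Hold the first coach session after that visit. Posttest is due within 7 days and sessions are every other week, so the first session still fits within the first 14-day interval.
- Define the averaging window for the posttest step count, the same for both groups, so that it ends before disclosure.

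This is a wording change with no added visit, staff or participants. The cost is that coach scheduling starts up to about a week later, so the maintenance period may begin with a few days in which no meeting is booked.
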